[name], PGY-1

Columbia Presbyterian Internal Medicine Program

CRC IRB Protocol, December 2010

Conventional Ventilatory Support versus Extracorporeal Membrane Oxygenation for Severe ARDS: a Trial within Multiple ECMO Centers

A. Study Purpose and Rationale

ECMO (extracorporeal membrane oxygenation) is a technology used in ICU settings to provide cardiopulmonary bypass that enables reduction of ventilatory settings while avoiding severe hypoxemia and hypercapnea; the potential harm of positive pressure ventilation in the forms of baro-trauma, volu-trauma and oxygen toxicity can potentially be avoided through this technology. Originally developed in the 1970s, ECMO has seen significant device improvements that may expand its future indications. At present, it is well proven in respiratory failure in neonates however its role in treating adults remains under question. A randomized controlled trial that definitively shows mortality benefit of ECMO as compared to standard intensive care therapy for adult patients with respiratory failure remains necessary.

Review of the Literature

RCTs in neonates provide convincing evidence for the use of ECMO, with a number needed to treat between three and four infants for a mortality benefit at 1 year⁴. In adults, three prior RCTs exist, two of which are dated studies that showed no benefit^{1,5}. The most recent RCT was the CESAR trial, in which adults in the UK with respiratory failure defined as a Murray Score >3 (see appendix 1) or pH <7.2 were randomized either to conventional therapy or to referral to one ECMO center. This trial showed a disability free survival benefit for ECMO center referral (63% mortality for standard therapy vs 47% in ECMO center referral group, p=0.03) (disability defined as severe disability—bedbound and unable to wash/dress self). Within the group randomized to referral to the ECMO center, only 75% of these patients ultimately received ECMO. Overall the study was limited in its ability to make conclusions regarding the benefit of ECMO itself rather than referral to an ECMO center. A RCT that investigates the mortality benefit of ECMO itself would provide more appropriate justification for the role of ECMO in adults with respiratory failure.

B. Study Design and Statistical Procedures

The proposed trial will be modeled largely after the recent CESAR trial with several important differences.

Firstly, a multi-center trial RCT involving solely ECMO centers would allow for recruitment of sufficient patients for statistical power, and would remove the potential confounding variable of the type of center encountered in the CESAR trial. This would more clearly characterize a survival benefit provided by ECMO itself.

Secondly, the study population will be narrowed to include solely the first definition of respiratory failure employed in the CESAR trial (Murray score >3). The pH <7.2 definition of respiratory failure will be eliminated, as inclusion of patients meeting this parameter who may or may not meet the first parameter potentially diversifies the study group in terms of disease process and pathophysiology to an extent that is difficult to predict. This study will focus on severe ARDS alone as defined by a Murray score >3, with or without hypercapneic respiratory failure.

Hypothesis

For patients with severe but potentially reversible hypoxemic respiratory failure (Murray score >3) secondary to ARDS admitted to a center with ECMO, ECMO will increase survival without severe disability at 6 months post-randomization by a proportion of 25% as compared to non-ECMO ICU management at these same centers (including vent management by a pulmonologist as well as ARDSnet protocol).

Methods

a. Conceptual and Operational Definitions:

Study outcome will be a composite outcome of survival without severe disability at 6 months. Severe disability will be defined as being bed-bound and unable to wash and dress oneself.

b. Study Design

The study will be a longitudinal, prospective, un-blinded, parallel-arm, multi-center, intention to treat, RCT, composed of centers with adult ECMO experience. Study subjects will include patients aged 18-65 admitted to these centers who are diagnosed with potentially reversible hypoxemic respiratory failure. Upon diagnosis with ARDS at the ECMO center, the components of the Murray score will be monitored every 2 hours. Once a Murray score >2.5 is obtained, the intensive care team will begin to profile the patient for the study and contact a study representative if the patient's consenting family member is willing to speak with them (the consenting family member will provide initial consent, then, once able the patient can choose whether or not to continue with the trial). Data collection for all study members will include demographics, diagnosis leading to ARDS, dates of hospitalization/ intubation/ extubation, dates of transfers/discharges, conditions at discharge, complications, cause of death, vent settings, blood gases, hemodynamic status, APACHE II, Murray lung score. Once a Murray score of 3.0 is obtained, the study subject will be randomized to conventional therapy or to ECMO. Given the large potential for other variables to significantly affect the primary outcome of mortality, randomization will be stratified in a fashion similar to that done in the CESAR trial. Stratification will be performed for age, hours of high P/high FiO₂, and number of organs failed (see Appendix 2).

Conventional therapy will include ARDSnet protocol vent management strategy with vent strategies guided by a pulmonologist. Data collection for the conventional management group will include time course, complications, and success with fulfillment of ARDSnet protocol (low-

volume, low-pressure with $P_{plat} < 30$). For the ECMO group, V-V ECMO with percutaneous cannulation will be used, with standardized lung rest vent settings (P_{pk} 20-25, P_{pl} 10-15, rate 10, FiO_2 30%), and ECMO will be continued until lung recovery is deemed obtained or until apparent irreversible multi-organ failure is attained. Data collection for the ECMO group will include cannulation information, flow, sweep, and pressure rates, and complications information.

c. Statistical Analysis:

The estimated mortality for severe ARDS is 70% (NIH ARDS network database). As with the CESAR trial, an estimate of 10% severe disability in both trial arms will be used. For sample size calculation, Alpha will be set at 0.05 and Beta at 0.2. An effect size of a 25% proportional disability free survival benefit (70% mortality \rightarrow 52.5 mortality, or 17% difference in mortality) is estimated, which mirrors the effect size observed in the CESAR trial; using chi square testing this equates to a n of 132 patients for each study group.

C. Study procedures:

Intubation

All patients in this study will have respiratory failure prior to randomization, such that intubation and mechanical ventilation will occur prior to the study.

ECMO placement and maintenance

V-V ECMO will be placed for all patients randomized to the ECMO group. This requires a surgeon placing large catheters into the neck, in to the internal jugular vein, through a small incision. This is a simple, brief surgical procedure requiring sedation and anesthesia. Once the ECMO catheter has been placed, sedation will be used in order to prevent the patient from awakening and removing or moving the ECMO catheter, which is sutured in place in the neck. The catheters placed in the neck will extract blood from the heart that will then be run through the ECMO circuit for the purpose of oxygenating the blood and removing carbon dioxide from the blood. The ECMO circuits consist of pumps, membrane oxygenators, and filters. Blood running through the ECMO circuit has an increased risk of clotting such that all patients put on ECMO will receive heparin in order to avoid clotting. The heparin used to avoid clotting creates an increased risk of bleeding. To ensure that the therapeutic effect of heparin is appropriate, coagulation studies will be performed using simple blood tests.

D. Study Drugs: N/A

E. Medical Devices:

ECMO device

The ECMO circuit includes a Stockert SIII servo-controlled roller pump, Medtronic tubing, Medtronic .8meter squared membrane oxygenator, Medtronic ECMOTherm heat exchanger, a Stockert SIII control desk with dual pressure monitors, and Transonics Systems HT110 bypass

flow meter. Stockert—Freiburg, Germany; Medtronic—Minneapolis, MN; Transonics—Ithaca, NY.

Ventilator

Puritan Bennett 840 ventilators will be used.

F. Study Questionnaires:

For the purpose of identifying the primary endpoint, a brief questionnaire will be completed via phone interview asking after the disability status of the patients 6 months after randomization. Two simple yes/no questions will be answered: is the patient bedbound? Is the patient able to dress and wash his/her self?

G. Study Subjects:

Patients for this study will include patients admitted by any means (either transferred patients or patients entering the hospital via the ED of the ECMO center hospitals) to the ECMO centers involved in the study. In all cases, ECMO will be initiated following randomization at the ECMO study center.

Inclusion criteria will include adult patients (18-65 yo) with severe but potentially reversible hypoxemic respiratory failure despite optimal conventional treatment at the same study centers providing ECMO. Respiratory failure as mentioned will be defined by Murray score >3.0

Exclusion criteria will include duration of high P (>30 cm Ppk) and/or high FiO₂ (>0.8) ventilation for >7 days, intra-cranial bleeding or any other absolute contraindications to heparinization, hypoxemic respiratory failure not fulfilling ARDS definition or hypoxemic respiratory failure deemed irreversible by a study consultant, moribund patients deemed to have minimal chance for survival regardless of chosen intervention as defined by a study consultant. ARDS related hypoxemic respiratory failure implies acute onset of a potentially reversible pathophysiology for which 'lung rest' allowing for low pressure/low FiO₂ vent settings may provide mortality benefit through avoidance of baro/volu-trauma and oxygen toxicity as well as avoidance of any degree of hypoxemia during the acute phase of disease; this is the rationale for excluding nonreversible and chronic hypoxemic respiratory failure.

H. Recruitment of Subjects:

As mentioned above, study subjects will be identified by ARDS diagnosis and by Murray score. Once an ARDS diagnosis is made, Murray score parameters will be monitored every 2 hours, and once Murray score is >2.5 , the patient's primary intensivist will then ask after the consenting family member as to the willingness to speak with a study representative.

I. Confidentiality of Study Data

A unique code will be created for each study participant for identification purposes and for data collection. Data will be secured in a secure location, only accessible by investigators.

J. Potential Conflict of Interest: Unknown.

K. Location of Study: Studies will be conducted entirely within the critical care areas of participating ECMO centers.

L. Potential Risks:

All study subjects will be severely ill patients admitted to intensive care units and thus the risk of death and complications will be extremely high.

M. Potential Benefits:

A modernized high standard of intensive care will be provided to all subjects.

N. Alternative Therapies: N/A

O. Compensation to Subjects: none

P. Costs to Subjects: none

Q. Minors as Research Subjects: N/A

R. Radiation or Radioactive Substances: N/A

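### The hypothesis claims a 25% proportional rise in disability-free survival, but the worked rates and 132 per arm rest on a 25% proportional fall in mortality

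*Protocol*

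**What the plan says.** The primary outcome is set in Protocol section B, Methods, part a: "Study outcome will be a composite outcome of survival without severe disability at 6 months". The Hypothesis in the same section puts the effect on that outcome: "ECMO will increase survival without severe disability at 6 months post-randomization by a proportion of 25" per cent, compared with non-ECMO intensive care at the same centres.

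Section B, part c (Statistical Analysis) gives the sizing inputs:

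- Control mortality: "The estimated mortality for severe ARDS is 70" per cent.
- Disability: "an estimate of 10% severe disability in both trial arms will be used".
- Error rates: "Alpha will be set at 0.05 and Beta at 0.2". Sidedness is not stated.
- Effect label: "An effect size of a 25% proportional disability free survival benefit".
- Effect in numbers, in the parenthesis directly after that label: mortality goes from 70% to "52.5 mortality, or 17% difference in mortality".
- Result: "using chi square testing this equates to a n of 132 patients for each study group".

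The section adds that this effect matches the one seen in the earlier referral trial, which section A reports as 63% against 47%.

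**The concern.** A 25% relative fall in a bad outcome and a 25% relative rise in the complementary good outcome are the same only when the two are equally common. Here the bad outcome is far commoner, so they differ widely. The Hypothesis and the effect label name the rise in the good outcome, while the numbers in the same sentence as the label describe the fall in the bad one.

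The hypothesis is what a review board approves and what the result will be set against. Taken at its word, it is a much smaller effect than the one used for sizing, and the 80% power does not belong to it. A null result could be cited against a 25% relative gain that the trial had little chance of detecting. A positive result would be compared with the wrong target.

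**Working it through.** **Inputs (section B, part c, unless noted).** Control mortality 0.70; ECMO mortality 0.525 (0.70 × 0.75); severe disability 10% in both arms; alpha 0.05; power 0.80; chi-square test; 132 per arm. The 25% relative increase comes from the Hypothesis. Two-sidedness is my assumption.

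**Formulas.** With p̄ = (p1 + p2)/2 and d = |p1 − p2|:

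- n = [1.960 √(2p̄(1 − p̄)) + 0.842 √(p1(1 − p1) + p2(1 − p2))]² / d²
- Continuity-corrected: n_c = (n/4) [1 + √(1 + 4/(n d))]²
- Power at N per arm = Φ{[d − 1.960 √(2p̄(1 − p̄)/N)] / √([p1(1 − p1) + p2(1 − p2)]/N)}; with the correction, d is replaced by d − 1/N.

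**Step 1: reproduce 132.** For 0.70 v 0.525, p̄ = 0.6125 and d = 0.175. Then n = (1.3504 + 0.5704)² / 0.175² = 120.5, and n_c = 131.7, which rounds up to 132. A one-sided test would give 95 (106 corrected), so 132 points to a two-sided corrected calculation on mortality alone. Power at 132 is 80% corrected and 83.5% uncorrected. The exact difference is 17.5 points, which the text gives as 17%.

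**Step 2: express that effect as a gain in the good outcome.**

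- Survival: 30% to 47.5%; 0.475/0.30 = 1.58, a 58% relative increase.
- Disability-free survival with 10 points of disability in each arm: 20% to 37.5%; 0.375/0.20 = 1.875, an 88% relative increase.

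Neither is 25%.

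**Step 3: take the hypothesis literally.** Multiply the control rate of the good outcome by 1.25 and find the power at 132 per arm. The base of the 10% disability is not stated, so both readings are shown.

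| Control to ECMO, good outcome | Basis | Power, uncorrected | Power, corrected | n per arm for 80% (corrected) |
|---|---|---|---|---|
| 30% to 37.5% | disability ignored | 25% | 21% | 623 (650) |
| 27% to 33.75% | 10% of survivors disabled | 22% | 18% | 728 (757) |
| 20% to 25% | 10% of all patients disabled | 16% | 13% | 1,094 (1,134) |

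A one-sided test would raise the uncorrected range to 25–36%. Reading the hypothesis as 25 percentage points does not give 132 either: that needs about 54–61 per arm (62–68 corrected).

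**Step 4: carry the stated mortality fall to the composite of death or severe disability.**

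- 10% of all patients: 70 + 10 = 80% v 52.5 + 10 = 62.5%. Power at 132 is about 89% (86% corrected).
- 10% of survivors: 70 + 0.10 × 30 = 73% v 52.5 + 0.10 × 47.5 = 57.25%. Power at 132 is about 77% (73% corrected).

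A 25% relative reduction in the composite itself is a different effect again. On the first reading, 80% v 60% needs 82 per arm (91 corrected).

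**The case against.** The strongest reply is that the intended effect is on the page. The effect label is followed at once by the mortality rates, 132 follows from those rates with 80% power, and the rates 30% v 37.5% and 20% v 25% appear nowhere. Section A also calls 63% v 47% a benefit in disability-free survival. That is a 25.4% relative fall in the bad outcome (1 − 47/63) and a 43% relative rise in the good one (53/37). The Protocol thus seems to use the survival label for a relative risk reduction. In addition, the chi-square test is of no difference, so its result does not depend on how the hypothesis is phrased, and a careful reader would look at the confidence interval and the absolute rates.

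Most of this stands. A reader might infer that the trial was sized for the wrong target and has only 16–25% power for its real aim. The documents do not support that: the only effect given in numbers is the mortality fall, and 132 is adequate for it. The low power belongs to the literal wording alone.

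The reply does not remove the contradiction. The Hypothesis section gives no rates, so a reader there has nothing to correct the wording with, and the label is wrong in both places. The reply also leaves open the composite, which is the primary outcome but whose rates are not given and did not enter the sizing.

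**Conclusion.** The point holds as a mislabelled effect scale. The Hypothesis and the effect label describe a 25% relative increase in disability-free survival. The worked rates and the 132 per arm describe a 25% relative reduction in mortality, 17.5 points, equivalent to a 58% relative rise in survival. The stated 80% power applies to the second and not to the first, for which it would be about 16–25% (13–21% corrected).

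These power figures assume a two-sided test at 0.05, and the lower end of each range assumes that 10% of all patients are severely disabled. No reading of the hypothesis sentence yields 132, but the numbers in the Statistical Analysis section suggest that the mortality reduction was meant.

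**What to change.** 1. In the Hypothesis and in the effect-size sentence, state the effect as a 25% relative reduction in mortality, from 70% to 52.5%, an absolute fall of 17.5 points (in place of 17%). Delete the label "An effect size of a 25% proportional disability free survival benefit".
2. Because the primary outcome is the composite, give the implied rates of death or severe disability in each arm, and say whether the 10% is of all patients or of survivors.
3. Restate the power of 132 per arm on that scale: 80% to 62.5%, about 89% (86% corrected); or 73% to 57.25%, about 77% (73% corrected). Do not substitute a 25% relative reduction in the composite, because 132 does not come from that effect.
4. State that the calculation is two-sided and continuity-corrected, if that is confirmed.
5. State that the trial is not powered for a 25% relative increase in disability-free survival. If that effect is in fact intended, the trial would have to be re-sized to about 620–1,130 per arm.

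Items 1 to 4 and the statement in item 5 are changes of wording with no change in enrolment. The cost is that the restated power falls slightly below 80% if the 10% refers to survivors.

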Appendix 1: Murray Score

0-4 severity index of ARDS (total points as per below divided by 4)

a) p/f (with FiO₂ at 100% for 20 mins): $\geq 300=0$ pts, 225-299=1pt, 175-224=2pts, 100-174=3, $<100=4$

-CXR: nl=0, 1 pt per quadrant

b) PEEP: $\leq 5=0$, 6-8=1, 9-11=2, 12-14=3, $\geq 15=4$

c) Compliance: (ml/cmH₂O): $\geq 80=0$, 60-79=1, 40-59=2, 20-39=3, $\leq 19=4$

d) Number of quadrants with infiltr on CXR (1-4)

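### Two-hourly Murray scoring, read with Appendix 1, implies up to 4 hours a day at 100% oxygen before the family is approached, and no sentence exempts the screening checks

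*Protocol*

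**What the plan says.** Three parts of the protocol bear on this.

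- **Frequency.** Section B, Methods, b. Study Design: "Upon diagnosis with ARDS at the ECMO center, the components of the Murray score will be monitored every 2 hours". Section H, Recruitment of Subjects, agrees: "Murray score parameters will be monitored every 2 hours".
- **Definition.** Appendix 1 builds the score from four components. The p/f component is to be taken with FiO2 "at 100% for 20 mins". No other condition for p/f appears anywhere in the document.
- **Order.** Once the score exceeds 2.5, Section H says that "the patient's primary intensivist will then ask after the consenting family member as to the willingness to speak with a study representative". Section B.b has the same sequence, with the family giving the initial consent.

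Time above FiO2 0.8 has two further uses. In Section G, more than 7 days of high-pressure and/or high-FiO2 ventilation is an exclusion. In Appendix 2, hours of such ventilation (0-48 or 49-168) form a stratification factor. Sections A and G both give avoidance of oxygen toxicity as part of the trial's rationale.

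**The concern.** A site that applies the two-hourly rule together with the Appendix 1 definition would put each monitored ARDS patient on 100% oxygen for 20 minutes at every check. That would be a trial-driven exposure in critically ill patients. It would begin before anyone has spoken to the family, and it would reach patients whose score never passes 2.5. It would also be an exposure of the kind that the trial hopes to reduce.

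The score triggers both the approach to the family and randomisation. A site that follows the appendix and a site that reads p/f from routine gases would be obtaining that trigger under different conditions, and the protocol gives neither a reason to change.

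**Working it through.** The protocol states no figure for this exposure, so there is none to reproduce. The check sets the rules side by side and works out what they imply.

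**Inputs**
- Interval between checks: 2 h (Sections B.b and H)
- Time at FiO2 1.0 per p/f measurement: 20 min (Appendix 1)
- High-FiO2 threshold: above 0.8 (Section G)
- Cuts: 48 h (Appendix 2) and 7 days = 168 h (Section G and Appendix 2)

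**Exposure if every check meets the Appendix 1 condition**
- Checks per day: 24 / 2 = 12
- Time per day: 12 × 20 min = 240 min = 4 h
- Share of time: 20 / 120 = 16.7%
- Over 48 h: 24 × 20 min = 480 min = 8 h
- Over 168 h: 84 × 20 min = 1,680 min = 28 h

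These are upper limits on added exposure. A patient already at FiO2 1.0 adds nothing.

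**Effect on the high-FiO2 clock** (assuming that measurement time counts and that hours are cumulated)
- Scoring alone would take 48 / 4 = 12 days to reach the stratum cut and 168 / 4 = 42 days to reach the exclusion cut.
- Nothing is added while the patient is already above FiO2 0.8. Nothing is added to the exclusion clock while peak pressure is already above 30, because Section G joins the two conditions with and/or.
- One day of checks can therefore move a patient across a cut only if the other hours already lie within 4 h of it.

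**Order relative to consent**
1. ARDS diagnosis: two-hourly checks start.
2. Score above 2.5: the family is first asked.
3. Family consent.
4. Entry score reached: randomisation.

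Every check up to step 2 precedes any approach.

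**Role of the film component**
Without film points the score cannot exceed (4 + 4 + 4) / 4 = 3.0, so the Section G criterion of a score above 3.0 cannot be met without a film. The component is needed, but Appendix 1 says nothing about how recent the film must be.

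**The case against.** The strongest reply is that the checks are described as monitoring. No sentence orders a fresh oxygen manoeuvre each time, and Appendix 1 gives no frequency. Section C, Study procedures, lists only intubation and ECMO, which suggests that the author had routine data in mind. On that reading nothing trial-driven precedes consent. Consent pages are also absent from this copy, so any wording there on screening or a waiver cannot be judged.

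This has force as to intent, but it does not remove the problem. The appendix is the only definition of the score, and a routine gas need not meet its oxygen condition. If routine data were meant, the protocol departs from its own definition without saying so. Either reading needs a correction.

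Other parts of the objection stand in full:

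- A reader might infer a new chest film every two hours, 12 a day, and hence a contradiction with the entry under R, which declares radiation not applicable. The documents do not support this. No sentence orders a film at each check, the latest clinical film can serve, and the contradiction appears only if study films are first read into the text.
- A reader might infer that scoring biases the treatment comparison. It comes before randomisation, so any shift of stratum falls on both arms alike. No effect on power or on the primary endpoint follows.
- A reader might call the oxygen condition a contradiction of the rationale. The rationale concerns sustained ventilator settings. A timed measurement condition sits awkwardly beside it, no more.

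**Conclusion.** The point holds for the oxygen component and the order of consent. The stated rules, followed as written, give up to 4 h a day at FiO2 1.0 (16.7% of the time). This starts before the family is approached and includes patients who never become eligible. The figure assumes that each two-hourly check is a full Appendix 1 score and that the patient would otherwise be below FiO2 1.0. The protocol neither confirms nor excludes the first assumption, and that gap is the defect.

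Whether this time counts towards the high-FiO2 hours is also unstated. That is a secondary matter: the effect is small and confined to patients near 48 h or 168 h. For films, all that is needed is a clarification of which film may be used.

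Because the conflict concerns a possible trial-driven exposure before consent, it should be settled before the protocol is put into use.

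**What to change.** Reconcile Sections B.b and H with Appendix 1, in wording only:

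1. State in B.b and H that checks before consent use blood gases and films already obtained for care, and that the latest clinical film may be used.
2. Place any measurement made only for the trial, including the Appendix 1 oxygen condition, after family consent.
3. State whether measurement time counts towards the high-FiO2 hours in Section G and Appendix 2.

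The measurement condition itself is for the clinical leads to settle; none is proposed here.

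The cost is some loss of comparability: the screening score above 2.5 and the entry score may rest on p/f taken under different conditions. One p/f band is 1 point of the total, or 1 / 4 = 0.25 of the score, and the step from 2.5 to 3.0 is two such points. The protocol gives no data on how often the change of condition would move a patient by a band, so the size of this loss cannot be stated. Sample size, endpoint and visit schedule are unaffected.

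### The protocol is inconsistent about its primary outcome: Methods b calls it mortality, while the Hypothesis, Methods a and Section F use 6-month survival without severe disability

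*Protocol*

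**What the plan says.** Four places in the protocol bear on which outcome decides the trial, and a fifth describes its background.

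- **Hypothesis (Section B):** "ECMO will increase survival without severe disability at 6 months post-randomization by a proportion of 25" percent.
- **Methods a, Conceptual and Operational Definitions:** "Study outcome will be a composite outcome of survival without severe disability at 6 months". The word 'primary' does not appear here.
- **Section F, Study Questionnaires,** introduces the telephone call this way: "For the purpose of identifying the primary endpoint, a brief questionnaire will be completed via phone interview asking after the disability status of the patients". Disability status is needed only for the composite, so this attaches the primary label to the composite.
- **Methods b, Study Design, and Methods c, Statistical Analysis:** Methods b gives as the reason for stratifying: "Given the large potential for other variables to significantly affect the primary outcome of mortality". No time point is given. Methods c states "The estimated mortality for severe ARDS is 70% (NIH ARDS network database"), then "an estimate of 10% severe disability in both trial arms will be used", and then "An effect size of a 25% proportional disability free survival benefit (70% mortality" falling to 52.5). The label is disability-free survival; the figures are mortality.
- **Section A, Study Purpose and Rationale:** says that what is still needed is "A randomized controlled trial that definitively shows mortality benefit of ECMO as compared to standard intensive care therapy".

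**The concern.** Death and the composite are different variables. A patient alive at 6 months but bed-bound and unable to wash and dress counts as a success on mortality and a failure on the composite. The protocol attaches the word primary to the composite in Section F and to mortality in Methods b, and sizes the trial on mortality figures.

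The identity of the primary outcome belongs in the protocol. An analysis plan that chose one of the two would still contradict part of this text. The trial is unblinded, so the deciding comparison should be beyond dispute before data accrue. If it is not, a result significant on one outcome only could be presented as the primary result, with a passage of the protocol to support it either way.

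**Working it through.** **Inputs.** From Methods c: control mortality 70%, ECMO mortality 52.5%, severe disability 10% in both arms, alpha 0.05, power 0.80, chi-square test, 132 per group. Sidedness is not stated; two-sided is taken because it reproduces 132. The denominator of the 10% is not stated either, so both readings are carried.

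**Step 1: reproduce 132.** With p1 = 0.70, p2 = 0.525, d = 0.175 and mean 0.6125:

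- n = [1.960·√(2·0.6125·0.3875) + 0.842·√(0.70·0.30 + 0.525·0.475)]² / 0.175² = (1.350 + 0.570)² / 0.0306 ≈ 120.5, so 121 without continuity correction.
- Corrected: (n/4)·[1 + √(1 + 4/(n·d))]² = (120.5/4)·[1 + √(1 + 4/21.08)]² ≈ 131.7, so **132**.

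The stated size comes from mortality alone with a continuity-corrected, two-sided test. The 10% disability figure does not enter.

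**Step 2: how closely the two outcomes move together.** Everyone who dies also fails the composite. With failure probabilities p_d for death and p_c for the composite, the correlation is √[p_d(1−p_c) / (p_c(1−p_d))].

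- 10% of all randomised: p_c = 0.70 + 0.10 = 0.80, correlation √(0.14/0.24) = 0.764.
- 10% of survivors: p_c = 0.70 + 0.10·0.30 = 0.73, correlation √(0.189/0.219) = 0.929.

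**Step 3: type I error if a win on either counted.** The calculation is a multinomial simulation (dead, severely disabled, neither), 132 per arm, both arms alike, two-sided 0.05, 400,000 trials.

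| Reading of the 10% | Either test, uncorrected | Either test, corrected |
|---|---|---|
| Of all randomised (70% + 10%) | 0.081 | 0.058 |
| Of survivors (70% + 3%) | 0.067 | 0.049 |

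A bivariate-normal calculation with the Step 2 correlations gives 0.080 and 0.067, in line with the uncorrected column. One test alone has a rate of about 0.050 uncorrected and about 0.034–0.037 corrected.

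**Step 4: how often the two tests disagree under the planned mortality effect.** Same simulation with mortality 70% v 52.5%.

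| Severe disability, control v ECMO | Disagree, uncorrected | Disagree, corrected |
|---|---|---|
| 10% v 10% of all randomised | 0.119 | 0.137 |
| 3% v 4.75% (10% of survivors: 0.10·0.30 and 0.10·0.475) | 0.105 | 0.117 |

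The direction depends on the reading. Power at 132 per arm, uncorrected, is about 84% for mortality. For the composite it is about 89% if the 10% is of all randomised (failure 80% v 62.5%) and about 77% if it is of survivors (73% v 57.25%). Under the first reading most disagreements are the composite winning alone (about 8.5% of trials against 3.4%, uncorrected).

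**The case against.** The strongest reply is that this is loose wording and not a rival endpoint. The Hypothesis, Methods a and Section F agree on the composite. Mortality is called primary once, in a clause that explains stratification and sets no test or time point. The document also uses mortality loosely elsewhere: Section A reports the CESAR trial's disability-free survival benefit as 63% v 47% mortality, and Methods c does the same with 70% and 52.5%. This stands as far as it goes, and it makes the composite the better supported reading. It does not remove the conflict, because the sample size follows exactly from the mortality figures and the primary label in Methods b is explicit.

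Four stronger readings are tempting, and the document does not support them.

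- *The false-positive rate exceeds 5%.* No section states that a win on either outcome counts. Even if one did, the rate is 4.9% in one of the four cases in Step 3, under the test that reproduces 132.
- *The tests will often disagree.* Disagreement reaches about 39–41% only if ECMO alone adds about 7 points of severe disability. Methods c assumes the same 10% in both arms, and no figure in the protocol supports such a rise.
- *Section A sets mortality as the endpoint.* It describes a gap in the evidence and does not define this trial's outcome.
- *The absence of an alpha split or testing hierarchy is itself a defect.* Those details may properly sit in a statistical analysis plan, which is not at hand. The point rests on the contradiction.

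**Conclusion.** The point holds as an inconsistency in the current text that should be corrected. Choosing the outcome after seeing the data is something the text leaves open; it is not a stated plan.

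The size is moderate because the two outcomes are strongly correlated. A win on either would raise the uncorrected rate from about 5% to 6.7–8.1%, and the corrected rate from about 3.4–3.7% to 4.9–5.8%. Under the planned effect the choice of outcome would change the decision in about one trial in seven to one in ten (10–14%). These figures assume two-sided testing at 0.05, 132 per arm with complete outcomes, 70% control mortality, and the 10% disability rate read either of all randomised or of survivors. The win-on-either rule is an assumption made to size the problem.

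**What to change.** Amend the wording in three places.

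1. **Methods b:** where the stratification sentence names mortality as the primary outcome, name survival without severe disability at 6 months.
2. **Methods a and c:** state that this single comparison of ECMO with conventional therapy, by intention to treat at two-sided 0.05, decides the trial, and that 6-month all-cause mortality is secondary.
3. **Methods c:** express and label the effect on the same outcome, and say whether the 10% is of all randomised patients or of survivors.

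The order of testing for mortality may be left to the statistical analysis plan.

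The clarification needs no new data and does not itself add patients. The small downside is that mortality could not be claimed as the confirmatory result if the composite fails. The third change does mean rerunning the sample size. With the same 17.5-point mortality difference and the same corrected formula, the composite needs 115 per arm if the 10% is of all randomised (failure 80% v 62.5%) and 155 if it is of survivors (73% v 57.25%), so 132 may or may not stand.
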